### 15.3 Appendix 3 - Fitzpatrick Skin Type Grading

The Fitzpatrick scale is a numerical classification that is widely used by dermatologists to classify a person's skin type by their response to sun exposure (Fitzpatrick, 1988).

Skin Type	Sunburn and Tanning History
I	Always burns easily; never tans (pale white skin)
II	Always burns easily; tans minimally (white skin)
III	Burns moderately; tans gradually (light brown skin)
IV	Burns minimally, always tans well (moderate brown skin)
V	Rarely burns, tans profusely (dark brown skin)
VI	Never burns (deeply pigmented dark brown to black skin)

### 15.4 Appendix 4 Specification of the Solar Simulator Output

A multiport solar simulator utilizing a 300 W xenon arc lamp fitted with 6 liquid light guides 8 mm in diameter and two filters (Schott WG 320/1 mm dichroic mirror and UG 11/1mm) will be used for this study.

The accuracy of the SPF measured is dependent on the absorbance characteristics of the sunscreen filtering system to be tested in conjunction with the source spectrum. Therefore, it is important to define the source by the spectral distribution of its erythema efficacy as well as its overall spectral irradiance characteristics.

Thus, the source spectra specification is described in terms of cumulative erythema effectiveness by successive wavelength bands from < 290 nm up to 400 nm. The erythema

effectiveness of each wavelength band is expressed as the percentage relative cumulative erythema effectiveness (% RCEE) and will fall within the limits defined in Table 1.

The spectral output of the solar simulator will have been confirmed within the past 18 months or after 3000 hours of lamp running time, whichever is sooner, or after changing any significant physical component of the solar simulator, by calibrated spectroradiometric measurement. The spectroradiometer used to measure the spectral output of the solar simulator will be fitted with a double monochromator and its resolution bandwidth will be  $\leq 2$  nm with measurements made in steps not exceeding the bandwidth. The spectroradiometer will have been calibrated within the past 18 months against standard light sources for its response to spectral irradiances, for its wavelength accuracy and for linearity of signal responses at all wavelengths over an irradiance range covering the actual source measurement range.

The total irradiance of the solar simulator will also be measured and must not exceed 1600 W/m^2.

The total radiometric proportion of the UVA II (320 nm to 340 nm) irradiance of the simulator will be  $\geq 20\%$  of the total UV (290 nm to 400 nm) irradiance. Additionally, the UVA I region (340 nm to 400 nm) irradiance will be  $\geq 60\%$  of the total UV irradiance.

**Table 15-3 - % RCEE acceptance limits for the UV solar simulator output**

Spectral Range nm	Measured % RCEE	
	Lower Limit	Upper Limit
< 290	-	<0.1
290 to 300	1.0	8.0
290 to 310	49.0	65.0
290 to 320	85.0	90.0
290 to 330	91.5	95.5
290 to 340	94.0	97.0
290 to 400	99.9	100.0

4.6.1	Adverse Events and Serious Adverse Events.....	18
4.7	Analysis of Other Variables	18
5	Changes to the Protocol Defined Statistical Analysis Plan	19
	Attachment 1: List of Data Displays.....	20

List of tables

Table 4-1	Fitzpatrick Skin Type.....	13
Table 4-2	Scoring of patch cells according to ICDRG.....	14

List of figures

Figure 1-1	Example layout of the patch on the dorsum (shown adhesive side down)	7
------------	--	---

Developmental cosmetic moisturizers (a serum, lotion and cream)

212378

Statistical Reporting and Analysis plan Amendment 1, Text Final v1.0, 03 Sep 2019

Abbreviation

Abbreviation	Term
AEs	Adverse Events
ANVISA	Agência Nacional de Vigilância Sanitária (The National Health Surveillance Agency)
BDRM	Blinded Data Review Meeting
eCRF	Electronic Case Report Form
cm ²	Centimeter squared
GSKCH	Glaxo SmithKline Consumer Healthcare
ICDRG	International Contact Dermatitis Research Group
ICF	Informed Consent Form
MED	Minimal Erythema Dose
MedDRA	Medical Dictionary for Regulatory Activities
MFG	Manufacturing Code
mL	Milliliter
N/A	Not Applicable
PD	Protocol Deviation
PT	Preferred Term
RAP	Reporting and Analysis Plan
SAE	Serious Adverse Events
SD	Standard Deviation
SOC	System Organ Class
TEAE	Treatment Emergent Adverse Event
UVR	Ultraviolet Radiation

The purpose of this Statistical Reporting and Analysis Plan is to describe the planned analyses and outputs to be included in the Clinical Study Report for Protocol 212378 v2.0, dated 08 August 2019.

1 Summary of Key Protocol Information

A cosmetic product that is freely available to the consumer must be safe when applied under normal or reasonably foreseeable conditions of use. As a general requirement, the safety and compatibility of a new formulation should be confirmed before it is commercialized.

Compatibility studies, performed as patch tests, aim to confirm the local tolerance of topical cosmetic products during the first application to the skin, therefore providing assurance that the product is safe for use under maximized conditions.

Photo-irritation assessments aim to demonstrate the absence of irritation potential of a product when applied to the skin and exposed to ultraviolet radiation (UVR). Photo-sensitization assessments aim to demonstrate the absence of allergic potential of a product applied to the skin when exposed to UVR.

The objective of this clinical study is to assess the photo-irritation and photo-sensitization potential of three developmental cosmetic formulations compared to a reference product (negative control) after duplicate, repeated semi-occlusive patch applications to healthy human subjects by following a conventional photo-irritation and photo-sensitization methodology under supervision of a dermatologist.

Photo-irritation potential will primarily be evaluated through the repeated occluded application and UV exposure of the study products over 3 weeks (induction phase). Photo-sensitization potential will primarily be evaluated through a subsequent semi-occluded application and UV exposure (challenge phase) after a 2-week rest period.

1.1 Study Design

This will be a single-center, randomized, evaluator (single) blind study in healthy adult subjects aged 18 to 65 years with no dermatological disorders and with a Fitzpatrick skin phototype II to IV to evaluate the cutaneous photo- irritation and photo- sensitization potential of three cosmetic facial skincare products. Approximately 80 healthy subjects will be screened to randomize at least 40 subjects to ensure at least 25 evaluable subjects complete the entire study.

The study will consist of three phases, a 3-week induction phase consisting of two parallel repeated 24 hour patch applications on the backs of healthy subjects (one of which is subsequently exposed to UV radiation upon patch removal, and evaluation of cutaneous responses of both sites after each patch removal); a 2 week rest phase; and a final challenge phase, consisting of two parallel 24 hour patch applications to naive sites (one set of which is subsequently exposed to UV radiation upon patch removal, and evaluation of cutaneous responses of both sites 24, 48 and 72 hours after patch removal).

[figure not shown]
The sequence of each of the test products to the cells within the patch system for each subject will be randomly assigned per the randomization sequences provided. The sequence of the products to the cells for each subject will remain the same throughout the induction phase, and a different sequence per the randomization provided will be provided for each subject for the challenge phase.

There will be a total of 5 different test areas, located on the back of each subject, which will be used in this study across the screening, induction and challenge phases:

- 1 test area to determine the provisional MEDu in screening;
- 2 test areas for test products and reference product (saline solution) in the induction phase (1 series will be exposed to UV radiation, the other series will not);
- 2 test areas for test products and reference product (saline solution) in the challenge phase (1 series will be exposed to UV radiation, the other series will not).

The 4 test areas in the induction and challenge phases will each undergo applications of an adhesive patch system. Within each patch system, there will be 6 circular cells, of which 4 will be used to host the study products and 2 will be left blank. In this study, each of the study products will be dispensed into 4 adjacent cells, in two duplicate series of patches, as per the randomization schedule. Three cells will be used for the test products (serum, lotion and cream) and a fourth for the reference product (saline solution).

Figure 1-1 Example layout of the patch on the dorsum (shown adhesive side down)

Two semi-occlusive patches with 6 cells labelled A-F will be used. Four cells (A-D) will be used in this study (1 for each test product and 1 for the saline solution). Two cells (E-F) will remain empty.

1.2 Study Objectives

The study objectives are as follows:

Objectives	Endpoints
Primary Objective	Primary Endpoint
To evaluate the cutaneous photo-Sensitization potential of three cosmetic facial skincare products compared to saline solution.	Proportion of subjects with a potential sensitization reaction which is considered photo-initiated.
Secondary Objectives	Secondary Endpoints
To evaluate the cutaneous photo-irritation potential of three cosmetic facial skincare products compared to saline solution.	Proportion of subjects with a photo-initiated reaction score of '+' or greater which not considered a potential sensitization reaction.
To evaluate the cutaneous sensitization potential of three cosmetic facial skincare products compared to saline solution.	Proportion of subjects with a potential sensitization reaction which is not considered photo-initiated.
To evaluate the cutaneous irritation potential of three cosmetic facial skincare products compared to saline solution.	Proportion of subjects with a non-photo-initiated reaction score of '+' or greater which is not considered a potential sensitization reaction.
Safety	
To evaluate the general safety of three cosmetic facial skincare products	Frequency and severity of Adverse Events

Success criteria:

A test product will be considered to have low photo-sensitization potential if the proportion of subjects with a potential photo-sensitization reaction are comparable for the test product and saline.

The hypothesis is that the study products will have low photo-sensitization potential. Therefore, it is expected that the vast majority of responses will be negative. No formal statistical comparison between product groups shall be made.

Developmental cosmetic moisturizers (a serum, lotion and cream)

212378

Statistical Reporting and Analysis plan Amendment 1, Text Final v1.0, 03 Sep 2019

1.3 Treatments

	Test Product 1	Test Product 2	Test Product 3	Reference product (Negative Control)
Product Name	Developmental Serum	Developmental Lotion	Developmental Cream	Saline Solution: Sodium Chloride (NaCl; 0.9%)
Pack Design	40 mL Pump Pack	50 mL Tube	50 mL Tube	500 mL
Product Manufacturing Code (MFC)	CCI [REDACTED]	CCI [REDACTED]	CCI [REDACTED]	N/A – Commercial Product
Application quantity	Dose: 0.02 mL/cm ² Each product will be dispensed into an individual cell within the patch system according to the randomization sequence for the induction phase and the challenge phase and removed/reapplied as per study schedule.			
Route of administration	Topical dermal application via semi-occlusive patch to the dorsum.			
Application Instruction	Applied on-site by technician			

1.4 Sample Size Calculation

Approximately 80 healthy subjects will be screened to randomize at least 40 subjects to ensure at least 25 evaluable subjects complete the entire study. No formal power calculations have been performed on this study. This sample size is standard in clinical testing practices and is consistent with the guidelines the National Health Surveillance Agency, 2012 (ANVISA).

2 Planned Analyses

2.1 Interim Analysis

No interim analysis is planned.

2.2 Final Analyses

The final planned analyses will be performed after the completion of the following sequential steps:

1. All subjects have completed the study as defined in the protocol.
2. All required database cleaning activities have been completed and database has been locked.
3. All criteria for unblinding the randomization codes have been met and the randomization codes have been distributed.

3 Considerations for data analyses and Data Handling Conventions

3.1 Baseline Definition

Baseline grading of naïve test sites will be performed prior to the patch application at Visit 4 Day 1 (induction phase) and Visit 19 Day 36 (challenge phase) using the scoring system detailed in grading scale [Table 4-2](#).

3.2 Subgroups/Stratifications

No subgroups or stratification factors are defined in this study.

3.3 Centers Pools

Since this is single centre study, pooling of centres is not applicable.

3.4 Timepoints and Visit Windows

The time points and visits for this study are defined in the section “Schedule of Activities” of the protocol. Any deviation from the study schedule may be reviewed on case-by-case basis at the Blinded Data Review Meeting (BDRM).

4 Data Analysis

Data analysis will be performed by Syneos Health. The statistical analysis software used will be SAS version 9.4 or higher.

Prior to database closure a BDRM will be conducted in which various aspects of the trial will be discussed and agreed.

Unless otherwise described, all listings will be produced for all randomized subjects.

4.1 Populations for Analysis

4.1.1 Subject Disposition

Screen failures are defined as subjects who consent to participate in the clinical study but are not subsequently randomized. An enrolled subject is a subject who has signed informed consent and is eligible to proceed beyond the screening visit. There are two randomizations; one is at Visit 4 for the induction phase and one at Visit 19 for the challenge phase. The number of subjects screened, enrolled and randomized in induction and challenge phase will be presented in [Table 14.1.1](#).

[Table 14.1.1](#) will also display the number and percentage of screen failure subjects (subjects not randomized in induction phase) with reasons why subjects are not randomized in induction phase. Percentages for screen failure subjects will be based on the total number of

subjects screened. The number and percentage of subjects not randomized in challenge phase will be displayed and percentages based on the number of subjects randomized in induction phase.

Subjects who complete the study (complete both induction and the challenge phases) and who discontinue during the challenge phase will be broken down by reason for discontinuation. The percentages will be based on the total number of subjects randomized in challenge phase.

The number and percentage of subjects in the safety population will also be summarized and percentages based on the number of subjects randomized in induction phase. The summary will be presented for all subjects (overall).

Subject disposition including demographic data (age, sex and race), screening date, phase, start date of study product and time, subject status (completer, Yes/No), study completion/withdrawal date, duration (in days) in the study (defined as: [(date of completion or withdrawal – start date of study product) + 1], duration (in days) of study product (defined as: [(last date and time of study product - start date and time of study product)+1]) and the primary reason for withdrawal will be listed ([Listing 16.2.1.1](#)) by phase for randomized subjects.

Subject disposition information will be listed for non-randomized subjects ([Listing 16.2.1.2](#)), displaying subject number, demographic information (age, sex and race), screening date, reason for screen failure and any further details of reason for screen failure.

4.1.2 Protocol Deviations

Protocol deviations will be tracked by the study team throughout the conduct of the study. Data will be reviewed prior to unblinding and closure of the database to ensure all important deviations are captured and categorised.

Important deviations of the protocol procedures may include, but will not be necessarily be limited to the following:

- Consent procedures
- Inclusion/exclusion criteria
- Non-compliance with product application
- Study procedures

The specific details of the important protocol deviations and how these will be assessed will be specified in the Blind Data Review Plan and subjects with important protocol deviations will be identified at the BDRM.

The number and percentage of subjects with at least one important protocol deviation will be presented overall and by type of deviation ([Table 14.1.2](#)) and listed in [Listing 16.2.2.1](#).

All protocol deviations collected on the protocol deviation case report form page will be listed in [Listing 16.2.2.2](#). The listing will present date of deviation, type of deviation and deviation description.

4.1.3 Analysis Populations

The analysis populations defined for this study are as follows:

Population	Definition / Criteria	Analyses Evaluated
Safety	The Safety population includes all randomized subjects who received at least one dose of any study product. This population will be based on the product sequence the subject received.	Primary endpoint, Secondary endpoints Safety
Randomized	All subjects randomized in induction phase regardless of whether they received study product. Any subject who receives a treatment randomization number will be considered to have been randomized.	Protocol deviations, disposition and medical history listings

NOTES :

- To be randomized into the challenge phase, a subject must have been already randomized in the induction phase. Therefore, the randomization status in challenge phase won't be considered to define the randomized population. Only the randomization in induction phase status will be used to define this population.
- Please refer to Attachment 1: List of Data Displays which details the population to be used for each of the displays being generated.

[Listing 16.2.3.1](#) will display all randomized subjects (induction phase) included and excluded from the safety population.

4.2 Subject Demographics and Other Baseline Characteristics

4.2.1 Demographic Characteristics

Descriptive statistics (number of subjects (n), mean, standard deviation (SD), median, minimum and maximum for continuous variables, frequency count (n) and percentage (%) of subjects for categorical variables) will be presented for demographic variables for all subjects (overall). These variables include age, gender, race and Fitzpatrick skin type will be presented for the safety population ([Table 14.1.3](#)).

Table 4-1 Fitzpatrick Skin Type

Skin Type	Sunburn and Tanning History
I	Always burns easily; never tans (pale white skin)
II	Always burns easily; tans minimally (white skin)
III	Burns moderately; tans gradually (light brown skin)
IV	Burns minimally, always tans well (moderate brown skin)
V	Rarely burns, tans profusely (dark brown skin)
VI	Never burns (deeply pigmented dark brown to black skin)

Demographic information will be listed ([Listing 16.2.4.1](#)) for all randomized subjects.

Mean Individual typology angle (ITA), Mean L and b, and Provisional Minimal Erythema Dose (MED) will be listed for each subject [Listing 16.2.4.3](#).

4.2.2 General Medical History

Medical history data will be listed ([Listing 16.2.4.2](#)) with start date and end date or ongoing at the start of the study.

4.2.3 Characteristics of Disease

N/A

4.3 Treatments (Study Drug, Rescue Medication, other Concomitant Therapies, Compliance)

Randomization details will be listed ([Listing 16.1.7.1](#)), including the randomization number, phase, randomization date, patch cell, planned randomized study product, and the actual study product received.

4.3.1 Study Drug Compliance and Exposure

Product application will be conducted at study site. Any protocol deviation associated with product applications will be reviewed during Blind Data Review Meeting prior to database lock.

4.3.2 Prior and Concomitant Medication

Prior or concomitant medication taken by or administered to a subject will be recorded in the case report form. The prior and concomitant medications will be coded using an internal validated medication dictionary, GSKDrug.

Prior medication will be listed by subject, with drug name, GSK drug synonym, dose, dose form, frequency, route, start date, study day relative to study product administration and end date ([Listing 16.2.4.4](#)). Prior medications are defined as those which stopped before the start date of study product. If the stop date is unknown or incomplete and the medication cannot be

considered as stopped prior to the start date of study product then the medication will be considered as a concomitant medication.

Concomitant medications will be listed similarly ([Listing 16.2.4.5](#)) with either ongoing or end date displayed. Concomitant medications are defined as medications that are ongoing or started on or after the start date of study product.

Unknown dates will not be imputed, however if the start or stop date is unknown, then it will be assumed to be concomitant medication unless the partial start date or stop date indicates differently.

4.4 Analysis of Endpoints

The primary and secondary endpoints will be derived based on the International Contact Dermatitis Research Group (ICDRG) scores at the UV-exposed and non-UV-exposed sites during the induction and/or challenge phase and the investigator assessment of potential sensitization at the final visit in the challenge phase (Visit 23, Day 40).

Positive reactions are defined as a score of ‘+’ or higher (that is, ‘+’, ‘++’, ‘+++’) on the ICDRG scale:

Table 4-2 Scoring of patch cells according to ICDRG

-	Negative reaction
+?	Doubtful reaction; faint erythema only
+	Weak (non-vesicular) positive reaction; erythema, infiltration and possibly papules
++	Strong (vesicular) positive reaction; erythema, infiltration, papules and vesicles
+++	Extreme positive reaction; bullous reaction, intense erythema and infiltration, coalescing vesicles
IR	Irritant reaction
NT	Not tested

The following order will be used to determine severity of ICDRG scores for classification of photo-initiated:

- “-” < “+?” < “+” < “++” < “+++”

“IR” has no impact on the severity of a score and IR can be selected by the investigator in addition to a positive reaction. Possible selections will be:

- either “-”, “+?”, “+”, “++”, “+++”
- either “+?”, “+”, “++”, “+++” and “IR”
- “NT” only

A subject (with at least one positive reaction) is classified as having experienced a photo-initiated reaction if the maximum score at the UV-exposed site for that subject is greater than the maximum score of the non-UV-exposed site for that subject.

Maximum score refers to the maximum across all visits for which a subject has data available during the relevant phase/phases as described in the individual endpoint definitions.

If “NT” is selected it will be handled in the same way as missing data. Only non-missing data will be considered in the determination of photo-initiated. If a subject discontinues prematurely, data up to the point of discontinuation will be used.

The assessment of positive reactions as potential sensitization reactions in the challenge phase will be determined by the blinded dermatologist and reported as:

- Yes
- No
- Unable to Determine

If “Unable to determine” is reported, it will not be counted as a potential sensitization reaction.

If a subject discontinues prior to the last visit the subject will not be considered for endpoints of sensitization or photo-sensitization, the subject can still be included in endpoints of irritation or photo-irritation based on ICDRG scores.

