4.4.1 Primary Endpoint

4.4.1.1 Primary Endpoint Definition

The primary analysis will be based on safety population.

The primary analysis will be based on the number of subjects with potential sensitization reactions considered photo-initiated (i.e. potential photo-sensitization reactions).

Potential photo-sensitization reactions are defined as a positive reactions meeting both of the following requirements:

- sensitization reported as “yes” at final visit of challenge phase (sensitization box ticked “yes” on eCRF)
- the maximum score of the UV-exposed site (across all visits) during the challenge phase > maximum score of the non-UV exposed site (across all visits) during the challenge phase

The number and percentage of subjects with potential sensitization considered photo- initiated reactions will be presented by product group in [Table 14.2.2.1](#). No formal statistical inference will be performed.

All potential sensitization reactions considered photo-initiated will be listed ([Listing 16.2.6.3](#)) for the safety population.

A frequency table will be presented for potential sensitization reactions (Sensitization (Yes), non-sensitization (No) and Unable to determine) regardless of photo initiation status by product group in [Table 14.2.1.1](#).

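### SAP 4.4 defines photo-initiation from subject-level maximum scores, so when two or more products react in one subject, one product's scores can cancel or create another's photo-initiated status

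*SAP*

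**What the plan says.** SAP 4.4 states the general rule with the subject as unit: "A subject (with at least one positive reaction) is classified as having experienced a photo-initiated reaction" when "the maximum score at the UV-exposed site for that subject is greater than the maximum score of the non-UV-exposed site for that subject". It then defines the maximum by time only: "Maximum score refers to the maximum across all visits for which a subject has data available during the relevant phase/phases". Neither sentence mentions product or patch cell.

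The primary definition in SAP 4.4.1.1 repeats the comparison for the challenge phase, as "the maximum score of the UV-exposed site (across all visits) during the challenge phase > maximum score of the non-UV exposed site", again without naming a product. The three secondary definitions in SAP 4.5.1 have the same form. Non-photo-initiated sensitisation uses the challenge phase alone, while photo-irritation and irritation use induction and challenge together.

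Each subject wears two patches, one irradiated and one not, and each patch holds all three test products and saline (SAP 1.1). The output is nevertheless by product: SAP 4.4.1.1 says the "reactions will be presented by product group", and SAP 4.5.1 does the same for the secondary endpoints. The success criterion (SAP 1.2) sets each test product against saline, which sits on the same backs.

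**The concern.** The unit of classification (subject) does not match the unit of reporting (product within subject). If the subject's overall UV and non-UV maxima decide the status of each positive product, a product's classification depends on how its neighbours scored. That can go wrong in both directions, and saline is one of the four products, so the comparator is exposed as well.

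No margin or test stands behind the success criterion; the proportions need only be comparable. One reclassified subject moves a product's percentage by 1/25 = 4 points with 25 evaluable subjects, or 1/40 = 2.5 points with 40. In a safety study the more worrying direction is a photo-initiated reaction that is cancelled and so not counted.

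**Working it through.** The plan has no power, error rate or effect size on this point, so there is no figure to reproduce. The check is of the rule itself.

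**Inputs from the documents.** Score order - < +? < + < ++ < +++, with '+' or higher positive (SAP 4.4); four products on each of two patches (SAP 1.1); at least 40 randomised and at least 25 evaluable (SAP 1.4).

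**Worked cases** (UV score / non-UV score):

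| Case | Product A | Product B | Subject maxima | Literal rule | Within product |
|---|---|---|---|---|---|
| Cancel | + / + | + / - | + vs + | B not photo-initiated | B photo-initiated |
| Create | + / + | ++ / - | ++ vs + | A photo-initiated | A not photo-initiated |

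**All score pairs for two products.** A product has 5 × 5 = 25 score pairs. Four have no positive score, leaving 21.
- Both products positive: 21 × 21 = 441 combinations. A given product's status is cancelled in 71 and created in 37. At least one product is misclassified in 2 × (71 + 37) = 216 (49%); the two errors never coincide. These are unweighted counts, not probabilities.
- One product positive, the other '-' or '+?' at each site: 21 × 4 = 84 combinations, none discordant. Two positive products in one subject are therefore necessary for an error.

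**Size under assumed rates.** None of these inputs is in the documents: products react independently; each of the four has a both-site reaction of equal grade with probability b and a UV-only reaction with probability u; grades are + 70%, ++ 25%, +++ 5% (f), with cumulative values F = 0.70, 0.95, 1.

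A UV-only reaction is lost when the highest both-site grade among the other three products is at least as high as every UV-only grade in that subject. With T(k) = 1 − (b+u)(1 − F(k)):

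P(lost) = Σ F(k) × { T(k)³ − [T(k) − b·f(k)]³ }

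- b = u = 1%: 0.70(0.994³ − 0.987³) + 0.95(0.999³ − 0.9965³) + (1 − 0.9995³) = 0.0144 + 0.0071 + 0.0015 = 2.3%
- b = u = 2%: 0.70(0.988³ − 0.974³) + 0.95(0.998³ − 0.993³) + (1 − 0.999³) = 0.0283 + 0.0141 + 0.0030 = 4.5%
- b = u = 5%: 0.70(0.97³ − 0.935³) + 0.95(0.995³ − 0.9825³) + (1 − 0.9975³) = 0.0667 + 0.0348 + 0.0075 = 10.9%

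The reverse error is smaller. At b = u = 5%, a both-site reaction is relabelled with probability 0.70(0.9825³ − 0.97³) + 0.95(0.9975³ − 0.995³) = 0.0250 + 0.0071 = 3.2%.

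**How often the precondition arises.** With p = b + u, the chance that a subject has two or more positive products is q = 1 − (1−p)⁴ − 4p(1−p)³, and the chance of at least one such subject among 40 is 1 − (1−q)⁴⁰.

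| b = u | p | q | At least one in 40 |
|---|---|---|---|
| 1% | 2% | 0.0023 | 9% |
| 2% | 4% | 0.0091 | 31% |
| 5% | 10% | 0.0523 | 88% |

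Meeting the precondition does not by itself mean that a product is misclassified.

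**The case against.** The strongest reply is that the SAP is loosely worded rather than wrong. Read purely literally, SAP 4.4 gives one status per subject, which cannot fill a by-product table. The harmful result needs product-level positivity combined with subject-level maxima, and the SAP does not spell out that combination. Much of the surrounding text points to a within-product comparison:

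- SAP Table 4-2 scores individual patch cells.
- Protocol 8.4.1 and 8.10.1 use the same product sequence on the irradiated and non-irradiated patches, so each UV cell has one matching non-UV cell.
- Protocol 4.2 and 12.2.6 classify individual positive reactions by where they occur, and SAP section 5 declares no change from the protocol analysis.
- SAP 4.4.1.1 and 4.5.1 speak of reactions and of the UV-exposed site in the singular.

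This stands as evidence of intent. A reader might infer that the by-product counts will be wrong; the documents do not support that, since a careful programmer may well pair the cells correctly. It does not rescue the wording. The only explicit general rule names the subject twice, and the protocol rule does not name the product either.

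A reader might also take 1 − (1−p)³ as the chance that a UV-only '+' is hidden, where p is the chance that another product is positive at its non-UV site. That gives 5.9%, 14.3% and 27.1% at p = 2%, 5% and 10%. These are upper bounds only, because other products' UV scores also enter the subject maximum and can keep it above the non-UV maximum.

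Finally, no inference is planned, and all grades, all positive reactions and the challenge-phase narratives are listed (SAP 4.5.1). A misclassification could therefore be found by inspection. That limits the harm but is no substitute for a correct derivation.

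**Conclusion.** The point holds as a defect in a stated derivation rule that should be corrected. As worded, SAP 4.4 allows one product's scores to cancel or create another's photo-initiated status, but only where at least two products are positive in the same subject.

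The practical size depends on reaction rates that the documents do not give. Under independence and the assumed grades, about 2%, 5% and 11% of true photo-initiated product reactions are lost at 1%+1%, 2%+2% and 5%+5%. Different grade patterns, or reactions that cluster within subjects, would change these figures.

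A reader might infer that the primary result is at serious risk. The documents do not support that: the SAP expects the vast majority of responses to be negative, and the primary endpoint also requires a sensitisation call of yes. A product with no positive reaction is never counted. The exposure is greater for photo-irritation and irritation, which take maxima over both phases and so give more chances for two products to be positive.

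**What to change.** - **SAP 4.4:** replace 'for that subject' with 'for that subject and product' in both places, and apply the condition of at least one positive reaction per product.
- **SAP 4.4.1.1 and 4.5.1:** the phrase 'for that subject' does not occur there, so insert 'for the same product'. Each maximum is then taken over the UV and non-UV cells that received that product in the relevant phase or phases.
- **Pooled endpoints:** state that matching across phases is by product and not by cell letter, because the product sequence changes between induction and challenge.

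Each product's status then depends only on its own scores, and both errors disappear. The cost is a SAP wording change and a matching line in the programming specification. Scores are already recorded by cell and the sequences are known, so no extra data are needed.
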